3.1.1.5. Serious Adverse Events

SAEs will be collected from the time the participant provides informed consent to 6 months after delivery for maternal participants originally randomized to BNT162b2 or through 1 month after the second dose of BNT162b2 for maternal participants who originally received placebo and subsequently receive BNT162b2. SAEs will be categorized according to MedDRA terms.

The primary safety endpoint “SAEs from Dose 1 through 1 month after delivery” will be summarized by SOC and PT at the participant level.

3.1.2. Immunogenicity Endpoints (Maternal Participants)

- SARS-CoV-2 neutralizing titers at 1 month after Dose 2 in maternal participants and nonpregnant women without serological or virological evidence (up to 1 month after receipt of the second dose) of past SARS-CoV-2 infection
- SARS-CoV-2 neutralizing titers at 1 month after Dose 2 in maternal participants and nonpregnant women with or without past SARS-CoV-2 infection

The maternal participants randomized to BNT162b2 group in this study and a group of nonpregnant female participants selected from the Phase 3 C4591001 trial who received BNT162b2 will be included in the primary analysis. The nonpregnant participants will be selected based on 1:1 age matching to the maternal participants.

Values below the LLOQ will be set to $0.5 \times \text{LLOQ}$ for the analysis. The LLOQ value for neutralizing titers will be included in the analysis specification once it is available.

3.2. Secondary Endpoints

3.2.1. Vaccine Efficacy Endpoints

- COVID-19 incidence per 1000 person-years of blinded follow-up based on central laboratory or locally confirmed NAAT in maternal participants without serological or virological evidence (prior to 7 days after receipt of Dose 2) of past SARS-CoV-2 infection
- COVID-19 incidence per 1000 person-years of blinded follow-up based on central laboratory or locally confirmed NAAT in maternal participants with or without evidence of past SARS-CoV-2 infection
- Incidence of asymptomatic infection of SARS-CoV-2 based on N-binding antibody seroconversion in maternal participants without serological or virological evidence of prior SARS-CoV-2 infection

3.2.2. Immunogenicity Endpoints (Maternal Participants)

- Full-length S-binding IgG levels at baseline, 2 weeks after Dose 2, 1 month after Dose 2, at delivery, and 6 months after delivery and fold rises in full-length S-binding IgG levels from baseline to each subsequent time point
- SARS-CoV-2 neutralizing titers at baseline, 2 weeks after Dose 2, 1 month after Dose 2, at delivery, and 6 months after delivery and fold rises in SARS-CoV-2 neutralizing titers from baseline to each subsequent time point

Values below the LLOQ will be set to $0.5 \times \text{LLOQ}$ for the analysis. The LLOQ value for full-length S-binding IgG will be included in the analysis specification once it is available.

3.2.3. Safety Endpoints (Infant Participants)

- Specific birth outcomes
- AEs from birth through 1 month of age
- SAEs and AESIs (major congenital anomalies, developmental delay) through 6 months of age

3.2.4. Immunogenicity Endpoint (Infant Participants)

- Full-length S-binding IgG levels at birth and 6 months after delivery and fold rise in full-length S-binding IgG levels from birth to 6 months after delivery

3.3. Exploratory Endpoints

3.3.1. COVID-19 Incidence Rate (Maternal Participants)

- COVID-19 incidence per 1000 person-years of follow-up based on central laboratory or locally confirmed NAAT from 7 days after the second dose of BNT162b2 in participants who received BNT162b2 at initial randomization

3.3.2. Asymptomatic SARS-CoV-2 Infection (Maternal Participants)

- Incidence of asymptomatic SARS-CoV-2 infection per 1000 person-years of follow-up based on N-binding antibody seroconversion in maternal participants who received BNT162b2 at initial randomization and without evidence of prior SARS-CoV-2 infection

3.3.3. Serological Responses by COVID-19 and SARS-CoV-2 Infection Status (Maternal Participants)

- Full-length S-binding IgG levels at baseline, 1 month after Dose 2, at delivery, and 6 months after delivery and fold rises in full-length S-binding IgG levels from baseline to each subsequent time point
- SARS-CoV-2 neutralizing titers at baseline, 1 month after Dose 2, at delivery, and 6 months after delivery and fold rises in SARS-CoV-2 neutralizing titers from baseline to each subsequent time point

These endpoints will be summarized by COVID-19 and SARS-CoV-2 infection status:

- Confirmed COVID-19
- Confirmed severe COVID-19
- SARS-CoV-2 infection but no confirmed COVID-19

3.3.4. Immune Response Between Dose 1 and Dose 2 (Phase 2 Maternal Participants)

- Full-length S-binding IgG levels at baseline and before Dose 2 and fold rise in full-length S-binding IgG levels from baseline to before Dose 2
- SARS-CoV-2 neutralizing titers at baseline and before Dose 2 and fold rise in SARS-CoV-2 neutralizing titers from baseline to before Dose 2

The pre-Dose 2 blood samples for immunogenicity will be drawn from maternal participants in Phase 2 only.

3.3.5. Immune Response by Breastfeeding Status (Infant Participants)

- Full-length S-binding IgG levels at birth and 6 months after delivery and fold rise in full-length S-binding IgG levels from birth to 6 months after delivery by breastfeeding status

3.3.6. Safety Endpoints by Breastfeeding Status (Infant Participants)

- AEs from birth through 1 month of age by breastfeeding status
- SAEs and AESIs (major congenital anomalies, developmental delay) through 6 months of age by breastfeeding status

3.3.7. COVID-19 Incidence Rate (Infant Participants)

- COVID-19 incidence per 1000 person-years of follow-up based on central laboratory or locally confirmed NAAT

3.3.8. MIS-C Cases (Infant Participants)

- MIS-C incidence per 1000 person-years of follow-up

3.4. Other Endpoints

All safety, immunogenicity, and efficacy endpoints described above will be summarized separately for participants with confirmed stable HIV infection.

3.5. Baseline and Other Variables

For maternal participants, measurements or samples collected prior to Dose 1 are considered the baseline data for the assessments. For infant participants, measurements or samples collected at birth are considered the starting time points for the assessments.

3.5.1. Demographics, Medical History, and Physical Examination

For both maternal and infant participants, the demographic variables are date of birth, sex (male or female, for infant participants only), race (black/African American, American Indian or Alaskan native, Asian, Native Hawaiian or other Pacific Islander, white), and ethnicity (Hispanic/Latino, non-Hispanic/non-Latino, not reported). In cases where more than 1 category is selected for race, the category “multiracial” will be created and used for analysis.

The maternal participants also have the demographic variable age at Dose 1 (in years), which is derived based on the maternal participant's birthday. For example, if the vaccination day is 1 day before the maternal participant's 19th birthday, the maternal participant is considered to be 18 years old. For maternal participants who were randomized but not vaccinated, the randomization date will be used in place of the date of vaccination at Dose 1 for the age calculation. If the randomization date is also missing, then the informed consent date will be used for the age calculation. The infant participants also have the demographic variable gestational age at birth (in weeks).

Medical history for maternal participants will be categorized according to MedDRA. Comorbidities that increase the risk for severe COVID-19 illness will be categorized based on medical history terms.

If the clinical assessment indicates that a physical examination is necessary to comprehensively evaluate the maternal participant at Visit 1 and the infant participant at birth, a physical examination will be performed and any findings recorded in the source documents and, if clinically significant, it will be recorded on the medical history CRF for maternal participants and on the AE CRF for infant participants.

3.5.2. E-Diary Transmission

For maternal participants, an e-diary will be considered transmitted if any data for the local reactions, systemic events, or use of antipyretic medication are present for any day. If all data are missing for all items on the e-diary for all 7 days after vaccination, then the e-diary will be considered not transmitted. E-diary data will not be collected from maternal participants originally assigned to placebo who subsequently receive BNT162b2 after delivery.

3.5.3. Prior/Concomitant Vaccines and Concomitant Medications

The following concomitant medications and vaccinations will be recorded in the CRF for maternal participants:

- All vaccinations received from 14 days prior to study enrollment until the 6-month follow-up visit for participants originally randomized to receive BNT162b2.
- Any medication taken to treat AEs from the signing of the ICD through the final study visit will be recorded in the CRF.
- Prohibited medications listed in the protocol, Section 6.5.1, will be recorded in the CRF to include start and stop dates, name of the medication, dose, unit, route, and frequency from the signing of the ICD through the final study visit.

The following concomitant medications will be recorded in the CRF for infant participants:

- Any medications taken to treat AEs and/or SAEs from birth (Visit 1) through the final study visit.

Prior and concomitant vaccines and concomitant medications will be coded using the WHO Drug Dictionary.

3.6. Safety Endpoints

Local reactions, systemic events, AEs, and SAEs have been described above in the primary safety endpoints. Specific birth outcomes and AESIs (major congenital anomalies, developmental delay) have been described above in the secondary safety endpoints.

4. ANALYSIS SETS (POPULATIONS FOR ANALYSIS)

Analysis populations are defined for the statistical analysis of safety, immunogenicity, and efficacy results in the table below. For the specified criteria in each population definition that are not associated with unblinded information (randomized vaccine or vaccine actually received), data for all participants will be assessed to determine if participants meet the criteria for inclusion in each analysis population prior to unblinding and releasing the database, and the classifications will be documented per standard operating procedures.

Population	Description
Enrolled	All participants who have a signed ICD.
Randomized	All participants who are assigned a randomization number in the IWR system.
Evaluable immunogenicity (maternal)	All participants who 
 are eligible and randomized; receive 2 doses of the vaccine to which they are randomized, with Dose 2 received within the predefined window (19-42 days, inclusive, after Dose 1); have at least 1 valid immunogenicity result within an appropriate window 1 month after Dose 2 (28-42 days, inclusive, after Dose 2); and have no other important protocol deviations as determined by the clinician.
Dose 1 evaluable immunogenicity (maternal)	All participants who 
 are eligible and randomized; receive Dose 1 of the vaccine to which they are randomized; have at least 1 valid immunogenicity result within an appropriate window 1 month after Dose 1 (19-23 days, inclusive); and have no other important protocol deviations as determined by the clinician.
Evaluable immunogenicity (infant)	All infant participants born to evaluable immunogenicity maternal participants and have no important protocol deviations as determined by the clinician.
All-available immunogenicity (maternal)	All randomized participants who receive at least 1 dose of the study intervention with at least 1 valid and determinate immunogenicity result after vaccination.
All-available immunogenicity (infant)	All infant participants born to all-available immunogenicity maternal participants.
Evaluable efficacy (maternal)	All eligible randomized participants who receive all vaccination(s) as randomized, with Dose 2 received within the predefined window (within 19-42 days after Dose 1), and have no other important protocol deviations as determined by the clinician on or before 7 days after Dose 2.
All-available efficacy (mITT) (maternal)	Dose 1 all-available efficacy: All randomized participants who receive at least 1 vaccination. Dose 2 all-available efficacy: All randomized participants who complete 2 vaccination doses.

Population	Description
All-available efficacy (mITT) (infant)	All infant participants born to Dose 1 all-available maternal participants.
Safety (maternal)	All randomized participants who receive at least 1 dose of the study intervention.
Safety (infant)	All infant participants born to maternal participants who receive at least 1 dose of the study intervention.

The important protocol deviations will be determined by the medical monitor. An important protocol deviation is a protocol deviation that, in the opinion of the sponsor's clinician, would materially affect assessment of immunogenicity/efficacy, eg, participant receipt of a prohibited vaccine or medication that might affect immune response or a medication error with suspected decrease in potency of the vaccine. The sponsor's clinician will identify those participants with important protocol deviations that result in exclusion from analysis populations before any unblinded analysis is carried out.

For all the immunogenicity endpoints, the analysis will be based on the evaluable immunogenicity population. An additional analysis will be performed based on the corresponding all-available immunogenicity population if there is over 10% difference in sample size between the all-available immunogenicity population and the evaluable immunogenicity population. Participants will be summarized according to the vaccine group to which the maternal participants were randomized.

The safety analyses will be based on the safety population. Participants will be summarized by vaccine group according to the study interventions the maternal participants actually received.

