Type of Visit	Clinic	Clinic	Clinic	Clinic	Hospital	Phone Call	Clinic	Clinic		
Assess acute reactions for at least 30 minutes after study intervention administration	X	X								
Provide/ensure participant has a thermometer and measuring device	X	X								
Review reactogenicity e-diary data (daily review is optimal during the active diary period of 7 days following study intervention administration)	↔	↔								
Review ongoing reactogenicity e-diary symptoms with participant and obtain stop dates		X	X							
Record pregnancy outcome information					X	X				
Record AEs and SAEs as appropriate ^f	X	X	X	X	X ^d	X	X ^d	X ^d	X ^d	X ^d
Collect e-diary or assist the participant to delete application								X		

Visit Number (Maternal Participants)	1	2	3	4	5	6	7	8	Unplanned	Unplanned
Visit Description	Screening: -28 Days to Vaccination 1	Vaccination 2	2-Week Post-Vaccination 2 Follow-up ^a	1-Month Post-Vaccination 2 Follow-up ^a	Delivery	1-Week Postdelivery Follow-up Call	1-Month Postdelivery Follow-up ^b	6-Month Postdelivery Follow-up For Participants Originally Randomized to Receive BNT162b2	Potential COVID-19 Illness Visit ^c	Potential COVID-19 Convalescent Visit
Visit Window (Days)	Day 1 Visit 1	19 to 23 Days After Visit 1	11 to 17 Days After Visit 2	28 to 35 Days After Visit 2	Varies	7 to 10 Days After Delivery	21 to 35 Days After Delivery	160 to 200 Days After Delivery	Optimally Within 3 Days After Potential COVID-19 Illness Onset	28 to 35 Days After Potential COVID-19 Illness Visit
Type of Visit	Clinic	Clinic	Clinic	Clinic	Hospital	Phone Call	Clinic	Clinic		
Collection of COVID-19-related clinical and laboratory information (including local diagnosis)									X	X

Abbreviations: EDD = estimated delivery date; HIV = human immunodeficiency virus; LMP = last menstrual period.

- The 2-week postvaccination follow-up and 1-month postvaccination follow-up visits will not be performed if delivery occurs before the visits. If delivery occurs before Vaccination 2, the second dose should be given as soon as possible after delivery. Once delivery occurs, the visit windows are calculated based on the delivery date.
- All maternal participants will be unblinded. Placebo recipients will be given BNT162b2 and move to follow the procedures in [Section 1.3.2](#).
- The COVID-19 illness visit may be conducted as an in-person or telehealth visit.
- Only AEs occurring up to 48 hours after each blood draw and nasal midturbinate swab collection must be recorded.

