9.3. Analysis Sets

For purposes of analysis, the following analysis sets are defined:

Population	Description
Enrolled	All participants who have a signed ICD.
Randomized	All participants who are assigned a randomization number in the IWR system.
Evaluable immunogenicity (maternal)	All eligible randomized participants who receive 2 doses of the vaccine to which they are randomized with Dose 2 received within the predefined window, have at least 1 valid and determinate immunogenicity result from the blood sample collected within an appropriate window, and have no other important protocol deviations as determined by the clinician.
Dose 1 evaluable immunogenicity (maternal)	All eligible randomized participants who receive Dose 1 of the vaccine to which they are randomized, have at least 1 valid and determinate immunogenicity result from the blood sample collected after Dose 1 and before Dose 2, and have no other important protocol deviations before Dose 2 as determined by the clinician.
Evaluable immunogenicity (infant)	All infant participants born to evaluable immunogenicity maternal participants and have no important protocol deviations as determined by the clinician.
All-available immunogenicity (maternal)	All participants who receive at least 1 dose of the study intervention with at least 1 valid and determinate immunogenicity result after vaccination.
All-available immunogenicity (infant)	All infant participants born to all-available immunogenicity maternal participants.
Evaluable efficacy (maternal)	All eligible randomized participants who receive all vaccination(s) as randomized within the predefined window and have no other important protocol deviations as determined by the clinician.
All-available efficacy (mITT) (maternal)	Dose 1 all-available efficacy: All randomized participants who receive at least 1 vaccination. Dose 2 all-available efficacy: All randomized participants who complete 2 vaccination doses.
All-available efficacy (mITT) (infant)	All infant participants born to Dose 1 all-available maternal participants.

Population	Description
Safety (maternal)	All randomized participants who receive at least 1 dose of the study intervention.
Safety (infant)	All infant participants born to maternal participants who receive at least 1 dose of the study intervention.

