2.1. Study Objectives, Endpoints, and Estimands

The estimands corresponding to each primary, secondary, and exploratory objective are described in Table 2 below.

In the primary safety objective evaluations, missing AE start dates will be imputed according to Pfizer safety rules (Section 5.3). No other missing information (eg, missing e-diary data) will be imputed in the safety analysis.

The estimands to evaluate the immunogenicity objectives are based on the evaluable immunogenicity populations (see Section 4 for definition). These estimands estimate the vaccine effect in the hypothetical settings where participants follow the study schedules and protocol requirements as directed. Missing antibody results will not be imputed. Immunogenicity results that are below the LLOQ will be set to $0.5 \times \text{LLOQ}$ in the analysis; this may be adjusted once additional data on the assay characteristics become available.

The estimands to evaluate the efficacy objectives are based on the evaluable efficacy populations (see Section 4 for definition). These estimands estimate the vaccine effect in the hypothetical setting where participants follow the study schedules and protocol requirements as directed. In addition, VE will also be analyzed by the all-available efficacy (mITT) populations. Missing laboratory results will not be imputed.

Table 2. List of Primary, Secondary, and Exploratory Objectives, Estimands, and Endpoints

Objectives ^a	Estimands	Endpoints
Primary Safety	Primary Safety	Primary Safety
To describe the safety and tolerability of prophylactic BNT162b2 when administered to maternal participants 18 years of age or older vaccinated at 24 to 34 weeks' gestation.	In maternal participants receiving at least 1 dose of study intervention from each vaccine group, the percentage of maternal participants reporting: 
 • Local reactions for up to 7 days following each dose • Systemic events for up to 7 days following each dose • AEs from Dose 1 through 1 month after Dose 2 • SAEs from Dose 1 through 1 month after delivery 	
 • Prompted local reactions (redness, swelling, and pain at the injection site) • Prompted systemic events (fever, fatigue, headache, chills, vomiting, diarrhea, new or worsened muscle pain, and new or worsened joint pain) • AEs • SAEs
Primary Immunogenicity	Primary Immunogenicity	Primary Immunogenicity

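### Reusing the 1-month evaluable set (result 28–42 days after Dose 2) for delivery, cord and 6-month antibody removes BNT162b2 mother–infant pairs whose birth came before day 28

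*SAP*

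**What the plan says.** SAP Section 4 requires evaluable mothers to "have at least 1 valid immunogenicity result within an appropriate window 1 month after Dose 2 (28-42 days, inclusive, after Dose 2"), together with eligibility, two doses as randomized with Dose 2 in window, and no important deviation. The evaluable infant set is "All infant participants born to evaluable immunogenicity maternal participants and have no important protocol deviations as determined by the clinician". The same section then states: "For all the immunogenicity endpoints, the analysis will be based on the evaluable immunogenicity population". The only separate evaluable set is the Dose 1 set for the pre-Dose 2 analysis (SAP 6.3.4).

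SAP 6.2.2.1.1 applies the maternal set at baseline, 2 weeks, 1 month, delivery and 6 months after delivery. SAP 6.2.4.1.1 and 6.3.5.1.1 apply the infant set at birth and 6 months.

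Protocol Section 9.3 is looser. It asks that mothers "have at least 1 valid and determinate immunogenicity result from the blood sample collected within an appropriate window", without tying the window to 1 month after Dose 2.

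On visits, Protocol Section 1.3.1 says: "The 2-week postvaccination follow-up and 1-month postvaccination follow-up visits will not be performed if delivery occurs before the visits". It adds: "If delivery occurs before Vaccination 2, the second dose should be given as soon as possible after delivery".

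There is one fallback: "An additional analysis will be performed based on the corresponding all-available immunogenicity population if there is over 10% difference in sample size". SAP 6.6.2.1 also has exclusions from each population summarized by reason and vaccine group.

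**The concern.** A 28–42 day window is the natural requirement for a 1-month titer. It has no bearing on whether a delivery or cord sample is valid. Applied to those endpoints, it removes women for lacking a sample that the protocol told sites not to take.

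This also sits badly with the estimand in SAP 2.1: "These estimands estimate the vaccine effect in the hypothetical settings where participants follow the study schedules and protocol requirements as directed". A woman dosed on time who delivers before day 28, and whose 1-month visit is therefore skipped, has followed the schedule as directed.

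What is at stake is the reach of the cord and delivery tables. The protocol synopsis lists antibody transfer to the infant among the study's aims. As written, the main BNT162b2 tables would describe essentially only births at least 28 days after Dose 2, and nothing in them would say so. Women first dosed near the upper end of the eligible 24–34 weeks would be largely absent.

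**Working it through.** The documents state no figure for this loss, so there is none to reproduce. The check has three parts.

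**1. Is there another scheduled in-window draw in the BNT162b2 arm?** The maternal schedule (Protocol 1.3.1) takes blood at Visits 1, 2 (Phase 2 only), 3, 4, 5 and 8, and at convalescent visits.
- Visits 3 and 4 are cancelled after delivery.
- Visit 5 is the delivery stay, so its sample is normally before day 28 when birth is before day 28.
- Visits 6 and 7 list no draw.
- Visit 8 is 160–200 days after delivery.

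No scheduled draw falls in days 28–42. Two incidental exceptions remain: a convalescent sample that happens to fall in the window, or a delivery-stay sample taken on or after day 28 following a birth just before it. Placebo mothers differ, because Visit 101 draws blood 21–35 days after delivery. Read by day count, that can fall in the window for births on days 0–21 after Dose 2.

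**2. Cut-off by arithmetic.** Inputs are gestational age (GA) at Dose 1 of 24 0/7 to 34 0/7 (Protocol 5.1.1), Dose 2 at day 21, and the window opening 28 days later.

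Earliest retained birth = GA at Dose 1 + 21 d + 28 d = GA at Dose 1 + 7 weeks.

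| GA at Dose 1 | Birth must be at or after |
|---|---|
| 24 0/7 | 31 0/7 |
| 27 0/7 | 34 0/7 |
| 30 0/7 | 37 0/7 |
| 32 0/7 | 39 0/7 |
| 34 0/7 | 41 0/7 |

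The 19–23 day visit window for Dose 2 moves each row by 2 days either way. Term births are therefore affected.

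**3. Size, by assumption.** The documents give neither GA at enrolment nor the delivery distribution. Assume delivery is normal with mean 39.0–39.5 and SD 1.3–1.9 weeks, in women undelivered at Dose 1.

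Chance that a pair is lost, P(birth < GA + 7 weeks):
- first dosed at 30 0/7: 3–15%
- first dosed at 32 0/7: 35–50%
- first dosed at 34 0/7: 78–94%

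Overall loss by simulation uses Dose 2 at day 21, phases weighted 200:150 and Dose 1 over 27–34 weeks (Phase 2) or 24–34 weeks (Phase 3). The placebo part of the pooled figure takes Visit 101 as uniform over days 21–35. Each cell is % lost in the BNT162b2 arm / pooled over both arms.

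| Delivery mean/SD (weeks) | Uniform | Early-skewed, Beta(1,2) | Late-skewed, Beta(2,1) |
|---|---|---|---|
| 39.0/1.3 | 25.3 / 22.1 | 9.0 / 8.2 | 41.7 / 36.0 |
| 39.0/1.9 | 26.6 / 22.7 | 11.7 / 10.3 | 41.6 / 35.1 |
| 39.5/1.3 | 19.6 / 17.6 | 6.1 / 5.7 | 33.2 / 29.5 |
| 39.5/1.9 | 21.6 / 18.6 | 8.6 / 7.7 | 34.5 / 29.5 |

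With about 175 women per arm, this is 0.061 × 175 ≈ 11 to 0.417 × 175 ≈ 73 pairs. Putting Dose 2 at day 19 or 23 throughout widens the BNT162b2 range to about 5–46%. Births at 37 weeks or later make up 50–94% of the lost pairs. Three of the four early-skewed scenarios have a pooled loss under 10%, so this rule alone would not trigger the all-available analysis there.

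**The case against.** The strongest reply is that the plan already copes. The all-available set is listed, as applicable, under the same main-analysis headings. The 10% trigger counts exclusions for every reason, so the three scenarios that fall short (5.7%, 7.7% and 8.2%) need only 2–4 further points from missed visits, late doses or deviations. Exclusions are reported by reason. This largely stands: the fallback will probably run. It is still conditional, and it admits anyone with one dose and any valid post-vaccination result. It therefore mixes one-dose, out-of-window and deviating women with the correctly dosed pairs of interest. Neither it nor the exclusion summary gives a clean estimate for those pairs.

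Second, a fixed cohort with an in-window 1-month sample is a defensible way to follow persistence in the same women, and the protocol leaves the window to the SAP. Both points are fair. There is no contradiction between the documents, and the fixed cohort is worth keeping as a supplementary table. It is a poor main basis for a cord-blood endpoint.

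Third, the size rests on assumed distributions. It falls to about 2–3% if every woman enrolled by 30 weeks (mean 39.0, SD 1.7). It rises above 50%, even with uniform enrolment, if Dose 2 came at day 42, the end of the SAP's own 19–42 day dosing window. The counts also treat every woman as otherwise evaluable, include HIV-infected women who are analysed separately, and include the few births before Dose 2 (0–8% of lost pairs). The range is conditional on its assumptions and is not a bound.

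Fourth, many participants may already have been unblinded when SAP version 3 was dated (31 March 2022), since enrolment ended on 25 October 2021 and unblinding comes 1 month after delivery. A change to the main set should therefore be documented as such.

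**Conclusion.** The concern holds. Barring incidental samples, a BNT162b2 mother who delivers before day 28 after Dose 2, and her infant, leave the main delivery, cord/birth and 6-month analyses, although the schedule was followed and their samples may be valid. This follows from the text and needs no assumption. The loss is about 20–27% of BNT162b2 pairs under uniform enrolment, 6–12% if early-skewed and 33–42% if late-skewed, given the assumed delivery distribution and Dose 2 at day 21.

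The consequence is limited. The 1-month GMR is untouched, the affected endpoints are secondary or exploratory and descriptive, and no between-arm antibody contrast is planned, so the arm difference created by Visit 101 distorts no comparison. Any bias in the geometric mean concentrations cannot be derived. It should be fixed because the main cord and delivery tables otherwise cover a narrower group than a reader would suppose.

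**What to change.** - Keep the 28–42 day requirement for the 1-month analyses, including the primary GMR.
- For the delivery, cord/birth and 6-month analyses (SAP 6.2.2, 6.2.4, 6.3.3, 6.3.5), define time-point-specific evaluable sets: eligible, two doses as randomized with Dose 2 in window, no important deviation, and a valid result at that time point.
- For the delivery and infant sets, also require that Dose 2 preceded birth, since the protocol allows it afterwards.
- Define infant evaluability from the mother's dosing and deviation criteria plus the infant's own valid sample.
- Tabulate delivery and cord results by days from Dose 2 to birth (for example <14, 14–27, ≥28), so that early and later responses are not merged in one figure.
- Retain the fixed 28–42 day cohort across time points as a supplementary table, and record the date and reason for the change relative to unblinding.

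The cost is new wording in SAP Section 4, one flag per time point and one interval variable, with no new data or visits. The downside is that denominators will differ by time point and must be shown in each table.
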